2 STUDY RATIONALE

In CF, the current estimated median age of survival is 37 years⁸⁴. The leading cause of shortened survival is progressive lung disease⁸⁵. Major accomplishments have been made in developing small molecule correctors and potentiators of CFTR, but a cure remains elusive. One would predict that intervening at the gene level with gene replacement therapy or at the protein level with CFTR potentiators and/or correctors early in that pathophysiologic cascade would result in improvements in downstream consequences, particularly at the level of the exuberant inflammatory response. However, recent clinical trials with drugs to improve CFTR function have not produced measurable improvement in airway inflammation despite improving lung function

and, at times, decreasing bacterial infection⁸⁶. As the pursuit for a cure continues, new and innovative therapeutic approaches are desperately needed to provide improved resolution of the on-going damaging infection and inflammation in the CF lung⁸⁷.

Bone marrow-derived hMSCs, which may ameliorate the consequences of CF, possess several advantageous properties ⁸⁸. First, hMSCs can be isolated from non-CF subjects by simple bone marrow aspiration and expanded in culture up to a billion fold within 8 weeks. This allows for potential wide-spread use of this therapy if hMSCs are found to be safe and effective. Second, hMSCs can differentiate into gut and respiratory epithelial cells^{89,90}, suggesting not just pulmonary, but systemic benefit. Third, hMSCs are immunoevasive because they lack major histocompatibility complex and co-stimulatory cell-surface antigens. Thus infusion of hMSCs from other humans is well tolerated⁹¹. Humans have received well over 20,000 infusions of hMSCs, both autogeneic and allogeneic, and there have been no episodes of tissue rejection or adverse reactions. Fourth, hMSCs have both anti-inflammatory and antimicrobial properties ⁸⁸. Our preclinical data suggest that hMSCs decrease bacterial burden and inflammation in a murine model of CF lung infection, and we have been able to demonstrate *in vitro* that the hMSCs have the capacity to enhance the effectiveness of antibiotics often utilized to treat the infections associated with CF¹⁹. Fifth, our studies also showed the unique capacity of the MSCs to cross species from humans into mice to demonstrate a beneficial effect without any major adverse effect.

The overall goal of this project is to determine the safety and tolerability of hMSCs and to explore efficacy endpoints for a subsequent clinical trial. Baseline studies for inflammatory markers in blood and sputum will be determined. This will be followed by a single infusion of hMSCs. These studies will be repeated at 7 and 28 days and compared to Baseline values (with-in subject comparison). If hMSC infusion is determined to be safe in this study, it could then be advanced to a Phase II double-blind, placebo-controlled clinical trial. If successful, hMSC therapy eventually could become part of a patient's therapeutic maintenance regimen. Such alternatives are sorely needed, because the data show that anti-inflammatory therapy is likely to ameliorate disease and prolong life, yet it is not applied to most patients due to concerns about adverse effects.

2.1 Risk / Benefit Assessment

While hMSCs are highly promising and supported by pre-clinical studies, they must be safe. The current data support their safety. While our proposal is the first for hMSCs in CF, there have been several other studies suggesting hMSCs are safe in COPD, idiopathic pulmonary fibrosis, bronchopulmonary dysplasia, acute respiratory distress syndrome, as well as many non-pulmonary diseases^{23,91}. There are 500 completed or on-going clinical trials using hMSCs, and a recent meta-analysis did not reveal any association between hMSC treatment and the development of acute infusion-related toxicity, organ system complications, infection (important for CF subjects), death, or malignancy ^{22,92}.

Our multidisciplinary team has extensive experience in isolating and expanding hMSCs. We are fortunate to collaborate with world-renown investigators from the NCRM, a multi-institutional, state-sponsored organization composed of investigators and clinicians from University Hospitals Cleveland Medical Center and Case Western Reserve University. Our collaborators have a 30 year history of adult stem cell research including the first in man studies of hMSCs and experience with studies similar to ours in patients with other chronic inflammatory diseases^{93,94}. We will be utilizing the NCRM Cellular Therapies Integrated Service to help with the preparation of cells and scale up from research to clinical operations.

Infusion with allogeneic hMSCs has been shown to be safe in follow-up periods lasting up to several years in patients with pulmonary disease and other inflammatory disorders including Crohn's disease, graft-vs.-host disease, multiple sclerosis, and type 1 diabetes²⁰. Up to 1×10^7 cells/kg have been infused safely. There have not been any issues with infusion-related toxicities or tumor development. Autopsy studies reveal limited

residual MSCs up to 18 months after administration²¹. A meta-analysis of clinical trials of MSC infusions to evaluate safety identified 1012 participants with varying clinical conditions²². The authors did not detect any association between hMSC infusion and acute infusion-related toxicities, organ system complications, infection, death or malignancy. However there was a significant association between MSCs and transient fever²².

A significant concern in CF patients receiving potent anti-inflammatory drugs is the increased risk of pulmonary exacerbations. Weiss and colleagues performed a placebo-controlled, randomized trial of mesenchymal stem cells in COPD where 31 subjects received four monthly stem cell infusions and there was no difference in hospitalizations for COPD exacerbations during the study (six in the MSC group and five in the placebo group)²³. A recent meta-analysis did not detect an association between MSC treatment and the development of infection²². Preliminary data in CF animals suggest improvement in infection related outcomes, not worsening^{18,19}. In our studies of CF mice infected with *P. aeruginosa*, there was a decrease in the bacterial burden in the animals that received hMSC infusions (Figure 1). No secondary spread or infectious complications were noted.

Another potential concern is the possible increased risk of cancer. Again, this has not been detected in clinical trials^{22,24}. However, the potential for malignant transformation would not be unexpected given some of the biologic similarities between stem cells and cancer cells. The risk of tumorigenesis is likely to be an extremely uncommon event with current culture conditions where cells are harvested for therapy well before the cultures reach senescence²⁰. Another potential risk could result if hMSCs engrafted for long periods of time leading to ectopic tissue formation and increased risk of malignant transformation. Autopsy studies did not detect hMSCs in follow-up studies. It appears that hMSCs work through a “hit and run” mechanism²¹. Despite these theoretical concerns, there have been no reports of *de novo* tumor formation complicating MSC infusion in humans^{22,24}. Nevertheless, in our protocol, cells will be passaged the minimum number of times to obtain sufficient cell yield to lessen potential for cytogenetic abnormalities, and any potential CF subjects with a history of invasive cancer requiring systemic therapy will be excluded from the study.

3 STUDY OBJECTIVES

3.1 Primary Objective

To evaluate the infusion-related safety and tolerability of a single allogeneic hMSC infusion in adults with CF.

3.2 Secondary Objectives

To explore preliminary evidence for the potential efficacy of hMSCs as a new therapeutic to treat CF pulmonary infection and inflammation as measured by

- Change in sputum inflammatory markers
- Change in serum inflammatory markers

To compare allogeneic hMSCs to autologous hMSCs in a preclinical model. The potential efficacy of MSCs obtained from CF subjects who agree to undergo the optional bone marrow aspiration will be evaluated in validated animal models.

3.3 Implications for Future Studies

This study is designed to address the safety and tolerability of a single hMSC infusion in subjects with CF. While in the background section we have focused primarily on the impact of MSCs on the pulmonary inflammatory response, hMSCs have potential to impact multiple other aspects of CF lung pathophysiology. MSCs also likely possess antibacterial properties. In our mouse models, hMSCs in combination with

gentamicin was more efficient in clearing bacteria than either therapy alone. This suggests the potential to use MSCs to enhance antibiotic regimens for acute pulmonary exacerbations in CF. In addition, because study subjects will be receiving hMSCs that do not possess a mutation in *cftr*, it is possible that hMSC infusion will provide a form of gene therapy. In future Phase III studies, we will evaluate the effects of hMSC infusion on outcome measures related to infection, inflammation and CFTR correction.

4 STUDY DESIGN

4.1 Study Overview

Overview of Study Design. A prospective, single-center, single-dose, dose-escalation, open-label interventional study to evaluate the safety and tolerability of allogeneic hMSCs in 15 clinically stable adult subjects with CF. Because the subject's own cells will contain two CFTR mutations, allogeneic hMSC infusion is being employed in this study. Screening data will be reviewed to determine subject eligibility. Subjects who meet all inclusion criteria and none of the exclusion criteria will be entered into the study. The Tables in Appendix II review the schedule of study visits. After a two to six week screening period, subjects will have the Baseline visit (Days 1-2) where they will undergo a single infusion of up to 5×10^6 allogeneic hMSCs/kg. The CCC and NCRM at Case Western Reserve University have a long-standing approach to identifying, screening and using donors to provide hMSCs. Donors are screened per FDA guidelines for cells and tissues (21 CFR 1271). The FDA guidelines are similar to those used for blood donation by Red Cross. The allogeneic hMSCs used in this study will come from one or two healthy donors who have been well-characterized by the CCC and whose sera test negative for CMV antibodies. Healthy donors will be followed by the PI or designee for any procedure-related AEs. Infusions will be performed in the Dahms Clinical Research Unit at University Hospitals Cleveland Medical Center. Study participants will be monitored for the development of infusion-related toxicities for 24 hours. Subjects will have subsequent study visits on Days 7, 14, 28, Months 3 and 6 and telephone calls on Days 4 (or 5), 21, 56 and Month 12. Subject safety and tolerability of the single dose of hMSCs will be evaluated at the study visits by reviewing subject diaries, interval histories, and subject questionnaires, performing physical examinations and spirometry, and obtaining safety laboratories. In addition to infusion related toxicities, special focus will also be placed upon detecting pulmonary exacerbations since an anti-inflammatory therapy theoretically could suppress the immune system to the point where it leads to increased infectious complications. Appendix I lists the criteria for a pulmonary exacerbation. This study will also explore efficacy endpoints that previously have been shown to be key regulators in CF and/or hMSCs: Serum inflammatory biomarkers (calprotectin, MPO, GM-CSF, IL-1 β , IL-6, IL8, IL-17, and TNF- α), and sputum inflammatory biomarkers (white cell counts with differentials, IL-1 β , IL-6, IL-8, IL-10, IL-17, GM-CSF, MIP-3 α , TNF- α , and active proteases including neutrophil elastase, α_1 -anti-trypsin, and MMP-9). These studies will be repeated on Days 7 and 28 and compared to Baseline values (with-in subject comparison). All subject samples will be archived for future studies to explore the impact on the microbiome and for future translational projects. Finally, an optional diagnostic bone marrow exam will be performed between screening and Day 1 on CF subjects willing to undergo the procedure, banked, and used for future translational studies.

The following treatment regimens will be used:

- Experimental treatment hMSCs at the following doses: 1×10^6 , 3×10^6 or 5×10^6 hMSCs/kg body weight

All subjects who begin an infusion of the investigational product will be considered evaluable for safety and efficacy analyses. Incidence of AEs will be monitored during the trial.

Safety assessments will be based on the incidence of AEs including protocol defined pulmonary exacerbations and changes in lung function, sputum microbiology, safety labs, subject questionnaire, and physical examination. An Acute Illness Visit will be arranged for any subject who experiences any abrupt change in baseline clinical status, between Visit 2 and Visit 5 (the 28 days following infusion) that in the estimation of an investigator, research coordinator, other health care provider or the subject necessitates an in-person office visit.

Total duration of subject participation in the study will be approximately 13 months. Long-term post-treatment follow-up will continue for 12 months after the infusion of the investigational product for each subject. Data on subject survival and on the occurrence of new health problems will be collected from all subjects who receive the investigational product infusion. The information will be gathered during a study visit, a routine clinic visit or via telephone. These data will be collected in the source documents (e.g., subject medical record) and transcribed into an electronic CRF. Any unsuccessful efforts to contact the subject (e.g., dates of unanswered phone calls, failure to show for a clinic visit, etc.) will be documented in the subject's source documents.

Total duration of conducting the study is expected to be approximately 24 months.

5 CRITERIA FOR EVALUATION

5.1 Primary Endpoint

The primary outcome will be the safety and tolerability of a single infusion of allogeneic hMSCs. Study participants will be monitored for potential dose limiting toxicities. The dose limiting toxicity (DLT) definition consists of the emergence of infusion-related allergic AEs as well as regimen related toxicities. For this study, a DLT will be considered for the occurrence in the first 24 hours after hMSC infusion of a grade ≥ 3 infusion-related allergic toxicities, which include rash, flushing, urticaria, dyspnea, fever $>40^{\circ}\text{C}$ ($>104.0^{\circ}\text{F}$) as scored according to the National Cancer Institute (NCI) Common Terminology Criteria for Adverse Events (CTCAE) version 4.0. Finally, the CTCAE will be used to assess and grade AE severity, including laboratory abnormalities judged to be clinically significant. In addition to infusion related toxicities, special focus will also be placed upon detecting pulmonary exacerbations since anti-inflammatory therapies theoretically could suppress the immune system to the point where it leads to increased infectious complications. Appendix I lists the criteria for defining a pulmonary exacerbation treated with antibiotics. All AEs encountered during the study period will be captured and graded.

In addition to DLT, safety and tolerability of a single infusion of allogeneic mesenchymal stem cells will also be determined by

- Incidence and severity of AEs
- Number of pulmonary exacerbations (modified Fuch's definition⁹⁵)
- Diary reports (Cystic Fibrosis Respiratory Symptom Diary)
- Changes in subject reported symptoms as captured by the Respiratory and Systemic Symptoms Questionnaire from Baseline (Visit 2) Day 1 to Baseline (Visit 2) Day 2, Visits 3, 4, 5, 6, and 7 and at times when a pulmonary exacerbation is being considered.
- Changes in physical examination
- Changes in vital signs including oxygen saturation checked throughout the infusion

- Changes in spirometry (FEV₁ %, FEV₁ (Liters), FEF₂₅₋₇₅) determined 30 minutes, 4 hours and 24 hours after completion of infusion and from Baseline (Visit 2) Day 1 to Baseline (Visit 2) Day 2, Visits 3, 4, 5, 6 and 7.
- Change in sputum quantitative microbiology (change in bacterial colony forming units between Baseline Day 1 and Day 7 and Day 28)
- Changes in hematology, comprehensive chemistry, erythrocyte sedimentation rate (ESR), high-sensitivity C-reactive protein (hs-CRP), and urinalysis results

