PRIMARY ENDPOINT	To evaluate safety and tolerability of a single infusion of allogeneic hMSCs as determined by: 
Dose limiting toxicity (DLT): A DLT is triggered by occurrence in the first 24 hours after hMSC infusion of grade ≥ 3 infusion-related allergic toxicities, which include rash, flushing, urticaria, dyspnea, fever $>40^{\circ}\text{C}$ ($>104.0^{\circ}\text{F}$) as scored according to the National Cancer Institute (NCI) Common Terminology Criteria

	
for Adverse Events (CTCAE) version 4.0 (http://evs.nci.nih.gov/ftp1/CTCAE/CTCAE_4.03_2010-06-14_QuickReference_8.5x11.pdf).
 
 • Incidence and severity of adverse events • Number of pulmonary exacerbations (modified Fuch's criteria⁹⁵) • Diary reports (Cystic Fibrosis Respiratory Symptom Diary (CFRSD)) • Changes in subject reported symptoms as captured by the Respiratory and Systemic Symptoms Questionnaire (RSSQ) from Baseline (Visit 2) Day 1 to Baseline (Visit 2) Day 2, Visits 3, 4, 5, 6 and 7 and at times when a pulmonary exacerbation is being considered • Changes in physical examination • Changes in vital signs including oxygen saturation checked throughout infusion • Changes in spirometry (FEV₁ %, FEV₁ (Liters), FEF₂₅₋₇₅) determined 30 minutes, 4 hours, and 24 hours after completion of infusion and from Baseline (Visit 2) Day 1 to Visits 3, 4, 5, 6 and 7 • Change in sputum quantitative microbiology (bacterial colony forming units between Baseline to Day 7 and Day 28) • Changes in hematology, comprehensive chemistry, ESR, hs-CRP, and urinalysis results
SECONDARY ENDPOINTS	
 • Change in blood inflammatory biomarkers from Baseline to Day 7 and Day 28 • Change in sputum inflammatory biomarkers from Baseline to Day 7 and Day 28
OTHER EVALUATIONS	
Bone marrow aspiration is optional. CF bone marrow aspirates will be used to assess autologous approaches to MSC therapeutics.
 
Any sputum or serum remaining after the study will be archived for future translational projects.

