1.3.6.1 Infusion-Related Toxicity

During this study, we plan to use freshly expanded hMSCs. By using freshly expanded hMSCs for the infusions, possible infusion-related toxicities will be reduced. However, there is a possibility that a subject may be unable to get fresh hMSCs on the day of the infusion. In this instance, we may infuse expanded hMSCs that have been frozen with dimethylsulfoxide (DMSO). Most studies have reported no infusion-related AEs. A patient with encephalopathy, stroke, and myocardial infarction most likely related to DMSO used in freezing medium has been reported⁵⁹. Anti-FBS antibodies are common but usually not clinically significant⁶⁰. One study reported a single participant who developed an urticarial rash following a second allogeneic MSC infusion⁵⁸. That participant had a 150-fold increase in anti-FBS antibodies after the second infusion. Because MSCs are relatively large cells (20-60 μ m)⁶¹ and cell clumping is possible, pulmonary embolism is a potential concern. No study has reported pulmonary symptoms, change in oxygen-saturation, or change in chest radiograph. Adherence to established procedures for thawing and infusing cells should minimize the potential for these AEs.

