8 STUDY TREATMENTS

8.1 Method of Assigning Subjects to Treatment Groups

In this Phase I open-label study, there is no placebo group. All subjects will receive a single infusion of hMSCs. 15 eligible subjects will be recruited from the adult CF Center located at Rainbow Babies and

Children's Hospital and will receive a single dose of one of the following doses of hMSCs: 1×10^6 , 3×10^6 or 5×10^6 hMSCs/kg body weight. A traditional 3+3 design will be utilized (Figure 4). If a maximum tolerated dose (MTD) is identified among the 3 doses, the next 3 subjects enrolled will receive the identified MTD. If there are no DLTs or one DLT, the next 3 subjects enrolled will receive same dose. If there are two or more DLTs, the next lower dose will be used as the MTD for the final 3 enrolled study subjects.

[figure not shown]

Figure 4. Study design for determining dose-limiting toxicity

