8.3.3 Dosage/Dosage Regimen

The first cohort of 3 subjects enrolled will receive a single infusion of 1×10^6 hMSCs/kg body weight. The second cohort of three subjects enrolled will receive a single infusion of 3×10^6 hMSCs/kg, and the third cohort of three subjects enrolled will receive a single infusion of 5×10^6 hMSCs/kg. The first subject in the subsequent cohort will not be enrolled until the last subject in the preceding cohort has completed Visit 5 (Day 28). There will be a minimum of 1 week between the dosing of each study subject in the first three cohorts. The final six subjects will receive a single infusion of 5×10^6 hMSCs/kg if that dose was well tolerated. If the highest dose was not well tolerated, then the final six subjects will receive the maximum tolerated dose (either 1×10^6 or 3×10^6 hMSCs/kg body weight).

Table 1: hMSC dose cohorts

Cohort 1	1×10^6 hMSCs/kg	3 subjects
----------	--------------------------	------------

Cohort 2	3×10^6 hMSCs/kg	3 subjects
Cohort 3	5×10^6 hMSCs/kg	3 subjects
Cohort 4	MTD	6 subjects

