9.1.9 Intravenous Infusion of hMSCs

Fresh MSCs are infused at Visit 2 (Day 1) from a syringe into a venous catheter followed by a saline wash. After the infusion of cells is complete, 10-ml of a normal saline flush is given immediately and a running IV of normal saline is maintained at 250 ml/hr for 4 hours. Subjects are monitored for 24 hours for infusion-related toxicity. Temperature, blood pressure, heart rate, respiratory rate and oxygen-saturation are measured prior to infusion and at 10 (\pm 5), 20 (\pm 5), 30 (\pm 5), 60 (\pm 15), and 90 (\pm 15) minutes and 2 hours (\pm 15 minutes) and 4 (\pm 15 minutes) hours post-infusion and then every 4 (\pm 15 minutes) hours for the remainder of the 24-hour observation period. Any toxicity is treated at the discretion of the managing physician, and toxicities are reported to the Principal Investigator, IRB, and FDA as appropriate.

MSC infusion has been very well tolerated. Although theoretically of concern, there have been no reported cases of immunosuppression, autoimmunity, cancer, significant lung damage, severe infection, or clinically significant ectopic tissue formation attributable to MSC infusion. MSC infusion could cause infection if the cells are contaminated. Strict aseptic technique during bone marrow aspiration, culture, thawing, and infusion and stringent microbiologic screening minimize this risk. Because of the immunosuppressive effects of MSCs, recipients potentially are at increased risk for infection.

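### The DLT definition in 5.1 names regimen-related toxicities, but the rule that is applied counts only allergic ones, so a severe non-allergic infusion event may not count toward the MTD

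*Combined protocol and SAP*

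**What the plan says.** Section 5.1 gives two accounts of a DLT in consecutive sentences. The first is general: "The dose limiting toxicity (DLT) definition consists of the emergence of infusion-related allergic AEs as well as regimen related toxicities". The second is the working rule. It counts events of grade 3 or higher under CTCAE 4.0 in the first 24 hours, and describes them as "infusion-related allergic toxicities, which include rash, flushing, urticaria, dyspnea, fever" (the fever being above 40 °C). The synopsis gives only the second account. It begins "A DLT is triggered by occurrence in the first 24 hours after hMSC infusion of grade" 3 or higher and continues with the same allergic list. Regimen-related toxicities are mentioned nowhere else in the visible text.

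The surrounding text is broader than allergy. The primary objective (3.1) is "To evaluate the infusion-related safety and tolerability of a single allogeneic hMSC infusion in adults with CF". Section 9.1.9 says "Subjects are monitored for 24 hours for infusion-related toxicity". Section 1.3.6.1 notes that "cell clumping is possible, pulmonary embolism is a potential concern".

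The count feeds the dose decision. For the expansion subjects, 8.1 keeps the dose after no DLT or one DLT, and otherwise: "If there are two or more DLTs, the next lower dose will be used as the MTD for the final 3 enrolled study subjects". Section 8.3.3 adds: "If the highest dose was not well tolerated, then the final six subjects will receive the maximum tolerated dose". Section 15.3 names the MTD among the three doses as the primary endpoint.

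**The concern.** A 3+3 design decides by counting, so it needs one definition of what is counted. Here the general sentence includes a class of event that the working rule leaves out. Two investigators applying 5.1 in good faith could count the same severe event differently and report different MTDs.

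The omitted class is not remote from this product. The protocol itself raises embolism from large or clumped cells. It also cites a report of stroke and myocardial infarction linked to DMSO, which is relevant only if frozen cells are used: 1.3.6.1 allows this, while 8.4.1 says the cells are used fresh. The 24-hour observation records blood pressure, heart rate, oxygen saturation and spirometry, and 15.3 plans to report systolic falls of 20 mmHg or more. Yet no visible DLT criterion covers severe hypotension, hypoxia or arrhythmia unless it is judged allergic.

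**Working it through.** **Events under the two readings**

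| Grade 3 or higher event within 24 h | General sentence, 5.1 | Working rule, 5.1 and synopsis |
|---|---|---|
| Urticaria, rash, flushing | DLT | DLT |
| Dyspnea judged allergic | DLT | DLT |
| Embolism with dyspnea not judged allergic | DLT if regimen-related | Unclear: dyspnea is listed, but the class is allergic |
| Hypotension, hypoxia, arrhythmia or stroke without allergy | DLT if regimen-related | Not clearly a DLT |

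**Effect on the dose (rule in 8.1).** Suppose two of the first three expansion subjects have a severe non-allergic infusion event.

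- General sentence: 2 DLTs. The final three subjects (3/15 = 20%) move to the next lower dose, and the MTD falls with them. From 5 to 3 × 10^6/kg is 1 − 3/5 = 40% lower; from 3 to 1 × 10^6/kg is 1 − 1/3 = 67% lower.
- Working rule: 0 DLTs. The dose and the MTD stay as they are.

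**How likely is it?** The plan states no DLT rate, so I used the earlier MSC trials that it describes:

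- 43 transplant recipients at 1–5 × 10^6/kg, no infusion-related toxicity (1.3.4.3.2).
- 30 COPD recipients at a fixed 100 × 10^6 cells per infusion, no infusion-related toxicity (1.3.4.1; section 1.3.2 says 31, which makes no difference here).
- 11 infused recipients with lysosomal or peroxisomal disorders, only self-limited grade 1 fever in 3 (1.3.4.3.3; the dose groups listed there add to 12, but the text says eleven were infused).

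Total: 43 + 30 + 11 = 84, with no grade 3 or higher infusion toxicity reported.

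- Exact one-sided 95% upper limit: 1 − 0.05^(1/84) = 0.035.
- P(2 or more of 3) = 3p²(1 − p) + p³. At p = 0.035 this is 3 × 0.001225 × 0.965 + 0.00004 = 0.0036, about 0.4%. At p = 0 it is 0.

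The limit covers every grade 3 or higher infusion toxicity, so it is an upper figure for the non-allergic part.

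**If the product were worse than expected.** Assume a standard 3+3, with no allergic events. A dose passes with probability (1 − p)³ + 3p(1 − p)² × (1 − p)³, where p is the rate of counted events. Under the working rule non-allergic events are not counted, so every dose passes with probability 1.00. If they are counted:

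| Assumed rate of severe non-allergic events | Dose passes |
|---|---|
| 10% | 0.91 |
| 20% | 0.71 |
| 33% | 0.43 |

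These rates are assumptions well above the 3.5% limit. They show what the wording would do, not what is expected.

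**The case against.** The strongest reply is that the specific sentence governs. It opens by saying what a DLT is for this study and gives grade, window and events; the synopsis agrees. On that view the general phrase is a leftover, and deleting it is an editorial matter. A narrow trigger with broad safety reporting is also a legitimate Phase I choice: 5.1 lists many other safety measures besides the DLT, and 15.3 tabulates grade 3 or higher events by dose cohort. The list is introduced in open terms, and dyspnea and high fever are not exclusively allergic, so many embolisms would probably be caught.

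Much of this stands, and it lowers the weight of the point. It does not remove it. Deleting the phrase ends the contradiction but leaves an MTD rule narrower than the stated objective and the monitoring. An open list still sits under the word allergic. The wider safety tables describe severe events without saying how they bear on the MTD. Nor does the well-tolerated condition in 8.3.3, which the visible text does not define.

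A reader might infer that an embolism would certainly be missed, or that subjects could be escalated past a severe event unnoticed. The documents support neither. Grade 3 or higher dyspnea is on the list, all AEs are captured and graded, and section 14 requires DMC approval before each next cohort. Figure 4, which carries the escalation scheme, is not visible, and the DMC Charter is not part of the documents, so nothing firm can be said about how they treat other severe events.

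**Conclusion.** The point holds as a defect in the decision rule that should be corrected. The rule as written omits a component that 5.1 says the DLT has, and the visible text does not say how a severe non-allergic infusion event affects the MTD. It matters for a rare but serious event; it does not imply frequent miscounting. The chance of the dose-changing case worked above is at most about 0.4%, provided that 84 recipients from different populations, with different donors and dosing, are a fair guide to adults with CF.

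Two stronger readings are not supported. A reader might rely on the 43-recipient trial alone, which gives an upper limit of 6.7% and a 1.3% chance; the protocol reports two further groups, and using them lowers both figures. A reader might also extend the point to the relatedness categories in Table 3 of 11.1. The DLT rule does not cite that table, 15.3 tabulates nothing by relatedness, and SAEs are documented whether or not related, so no planned result would change.

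**What to change.** In 5.1 and the synopsis, use one definition: a DLT is any CTCAE grade 3 or higher infusion-related toxicity within 24 hours of the infusion, allergic or not, with the present list kept as examples. Delete the undefined regimen-related term, which the new wording makes unnecessary. Check that Figure 4 uses the same definition.

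The cost is an amendment to the DLT text in two places, with no new visits, tests or analyses. Grade 3 or higher events already recorded within 24 hours of an infusion would need a re-check against the new wording. The real downside is that a coincidental CF event judged infusion-related could count as a DLT and lower the MTD.
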